DBS Deep Brain Stimulation

DSMB Data Safety Monitoring Board

EKG Electocardiogram

EQ-5D Euro-Qol 5D

EU European Union

FDA US Food and Drug Administration Code of Federal Regulations Title 21

21CFR

EudraCT European drug regulatory affairs Clinical Trials

GCP Good Clinical Practice

IB Investigator's Brochure

IC Informed Consent

ICH International Conference on Harmonisation of Technical Requirements for

Registration of Pharmaceuticals for Human Use

iMCQ Institute for Medical Technology Assessment Medical Consumption

Questionnaire

IMP Investigational Medicinal Product

Version 7: 23-10-2019 7 of 48

IMPD Investigational Medicinal Product Dossier

INVEST Infusion Versus Stimulation

iPCQ Institute for Medical Technology Assessment Productivity Cost

Questionnaire

MDS-UPDRS Movement Disorder Society's Unified Parkinson's Disease Rating Scale

METC Medical research ethics committee (MREC); in Dutch: medisch ethische toetsing commissie (METC)

MINI Mini-International Neuropsychiatric Interview

MRI Magnetic Resonance Imaging

NFU Nederlandse Federatie van Universitaire Medische Centra

NSTAPS The Netherlands SubThalamic and Pallidal Stimulation

PD Parkinson's Disease

PD-CRS Parkinson's Disease Cognitive Rating Scale

PDQ-39 The 39-Item Parkinson's Disease Questionnaire

PEG Percutaneous Endoscopic Gastrostomy

PIN Patient Identification Number

PT Prothrombin Time

PROAPD Patient-reported outcome tool for advanced Parkinson's disease

QALY Quality Adjusted Life Year

RCT Randomized Controlled Trail

RvZ Raad voor de Volksgezondheid

(S)AE (Serious) Adverse Event

SPC Summary of Product Characteristics (in Dutch: officiële productinfomatie

IB1-tekst)

Sponsor The sponsor is the party that commissions the organisation or

performance of the research, for example a pharmaceutical

company, academic hospital, scientific organisation or investigator. A party that provides funding for a study but does not commission it is not

regarded as the sponsor, but referred to as a subsidising party.

STN Subthalamic Nucleus

SUSAR Suspected Unexpected Serious Adverse Reaction

Wbp Personal Data Protection Act (in Dutch: Wet Bescherming

Persoonsgevens)

WTP Willingness-to-pay

WMO Medical Research Involving Human Subjects Act (in Dutch: Wet Medisch-

wetenschappelijk Onderzoek met Mensen

Version 7: 23-10-2019 8 of 48

SUMMARY

Rationale: Both Continuous intrajejunal Levodopa Infusion (CLI) and Deep Brain Stimulation (DBS) are accepted therapies for the treatment of advanced Parkinson's disease (PD). Neurologists and patients tend to prefer the more expensive CLI although a scientific rationale is lacking. To determine the optimal treatment in advanced PD, a comparative study of CLI and DBS is warranted.

Hypothesis: We hypothesize that CLI is a more expensive therapy in advanced PD than DBS and that the surplus in costs is not cost-effective with regard to benefits for the patient and caregivers in quality of life, PD symptoms and adverse events.

Objective: To realize a cost-effective treatment strategy in advanced PD.

Study design: Prospective, randomized, open label multicentre trial, with two additional observational patient preference treatment arms ("patient preference randomized trial"). **Study population:** Patients with PD who, despite optimal pharmacological treatment, have severe response fluctuations, dyskinesias, painful dystonia, or bradykinesia. A total of 66 patients will be randomized, at least120 patients will be included in the patient preference arms.

Intervention: Patients will be randomized to DBS or CLI. For DBS treatment, 2 electrodes will be implanted in the brain. The electrodes are connected to an implanted pulse generator, which will be placed subcutaneously in the subclavian area. For CLI treatment, a tube will be placed in the jejunum via a percutaneous endoscopic gastrostomy (PEG). This tube is connected to an external pump that delivers the levodopa-gel.

Main study parameters: There are 8 specified assessment visits for the patients in the randomized trial: at baseline, and 1 week, 3, 6, 9, 12, 24 and 36 months after start of the study treatment. The primary health economic outcomes are the costs per unit on the PDQ-39 and the costs per QALY for the cost-effectiveness and cost-utility analyses, respectively. The EQ-5D will be applied as the utility measure. Among the secondary outcomes are neurological impairments, functional health, care use and perceptions of patients and neurologists regarding both treatments.

Nature and extent of the burden and risks associated with participation, benefit and group relatedness: The study investigates the cost-effectiveness and cost-utility comparing CLI and DBS. Both treatments are currently available for advanced PD and both have a small risk of severe side effects. The surplus in burden of study participation compared to the regular treatment consists of a more detailed assessment procedure. The additional time for these extra assessments — consisting of questionnaires and motor symptom assessments — is approximately 15 hours, including time to travel. Besides this small burden the study has no additional risk compared to standard practice, which constitutes a negligible risk

Version 7: 23-10-2019 9 of 48

according to the NFU (Nederlandse Federatie van Universitaire Medische Centra) criteria for human research.

1. INTRODUCTION AND RATIONALE

Parkinson's disease (PD) is a neurodegenerative disease affecting the motor, autonomic, cognitive, and sensory systems. It is a disease of the elderly: above the age of 55 years, the prevalence of PD is 1.4%.[1] In 2011, almost 60.000 patients in the Netherlands were estimated to have PD and due to ageing of the population an increase of at least 50% is expected in the following years.[2] PD is one of the diseases causing the largest reduction in quality of life and social functioning and the ability to work are impaired.

The core symptoms of PD are caused by the degeneration of dopamine producing neurons. At present there is no cure for PD, but several symptomatic therapies are available that mainly act upon the motor symptoms. Most of these (i.e., tremor, rigidity and bradykinesia) initially respond well to oral dopamine replacement although dyskinesias frequently occur after a variable period. Patients with advanced PD frequently show rapid and seemingly unpredictable swings between mobility, often with dyskinesias (ON-phase), and immobility (OFF-phase).[3] In the Netherlands, the prevailing treatment options for these patients are Deep Brain Stimulation (DBS) and Continuous intrajejunal Levodopa Infusion (CLI).[4] Continuous apomorphine infusion (CAI) is gaining more ground as another treatment option, since this treatment was researched in a recent double blind randomised controlled trial.[5]

For DBS, a neurosurgeon places two electrodes in the brain. These are connected to an implantable pulse generator. Patients continue with PD medications, though often at a lower dose.

For CLI, a gastroenterologist places a tube in the jejunum, which is connected to a portable pump. A levodopa-gel is continuously administered through the tube. In general, patients with CLI may stop other PD medications. Similar to DBS treatment, patients are hospitalized for placement of the tube and for the start of the levodopa-gel treatment. In both treatments, patients regularly visit the outpatient clinic to adjust the treatment.

Another treatment option for patients with advanced PD is Continuous subcutaneous Apomorphine Infusion (CAI). In the Netherlands CAI is used in a smaller number of patients. CAI is not included in this research protocol, because at start of this trial, the evidence for effectiveness of CAI was of poor quality. Besides, CAI is slightly more expensive than DBS. A study that directly compares all three treatments is not feasible because of the large sample size needed.

Both treatment with DBS and CLI is expensive. We estimate that DBS equipment and batteries cost €10,000 per patient/year and CLI equipment and infusion solutions cost

Version 7: 23-10-2019 10 of 48

€45,000 per patient/year. In addition, patients need surgery and they frequently visit the clinic. In a recent Spanish study the mean cumulative 5-year cost per patient (including the surgery) was estimated € 88,014 for DBS and € 233,986 for CLI. [6]

Several level I studies have shown that DBS is efficacious for the treatment of PD motor symptoms: it reduces dyskinesias and motor fluctuations.[7] CLI reduces off-time and is effective for the treatment of motor fluctuations and dyskinesias as was shown in a few small and one larger level I trial. Both therapies significantly improve quality of life.[7-13] No head-to-head comparison of DBS and CLI has been performed, but when comparing individual studies, the effects on quality of life are similar.[8, 13] Little is known about comparative adverse-effects profiles of the therapies. One retrospective study suggests a higher rate of complications in CLI.[14]

The lack of comparative knowledge is reflected in the current CBO-guideline for PD (2010), which states no preference for one of the therapies.[4] Both DBS and CLI are available in the Netherlands and both are covered by the basic health insurance. After the introduction of CLI in 2007, the number of patients with PD receiving the traditionally standard treatment DBS initially slightly decreased, while the number of patients receiving CLI has increased, resulting in an approximately equal number of yearly DBS and CLI procedures in the Netherlands at the moment (80 each). [15] Currently, an estimated 600 PD patients have DBS and 300 patients are treated with CLI in the Netherlands. At present, there is unwanted variation in medical practice. Surveys we performed showed that out of 287 Dutch neurologists (response 50.5%), 45% prefers CLI and 35% prefers DBS. In 62 PD patients from a regional branch of the Dutch Parkinson Association only treated with oral medication, 40% prefers CLI, against 9% preferring DBS and 51% without preference.

That both patients and neurologists tend to prefer CLI over the traditionally standard treatment DBS, is of interest considering the lower level of evidence of CLI, but also given

In this comparative study between DBS and CLI we will assess the cost-effectiveness of both treatment options in advanced PD. Results of the INVEST study will probably lead to an unambiguous practice guideline. The resulting more efficient care may facilitate treatment with DBS in the more early stage of the disease process.[12]

the fact that CLI probably is much more expensive than DBS.

Version 7: 23-10-2019 11 of 48

2. OBJECTIVES

2.1 Primary Objective

To realize an efficient allocation of resources to the available treatment options in advanced PD, while guaranteeing the highest standard of care.

For the primary objective the following research questions will be answered:

- 1. What are, in the Netherlands, the direct and indirect costs and benefits of CLI and DBS as the two prevailing treatment options for advanced PD?
- 2. Is CLI cost-effective in advanced PD when compared to DBS?
- 3. With regard to the implementation, what are the perceptions about the two therapies in advanced PD in patients and neurologists and do they correspond to the actual figures on burden of the procedure and care, the effects, adverse events and costs?

2.2 Secondary Objectives

Secondary objectives are to compare motor and non-motor symptoms, quality of life, and daily functioning, adverse effects and complications between treatment with DBS and CLI.

Version 7: 23-10-2019 12 of 48

3. STUDY DESIGN

A prospective open label multi-centre randomized controlled trail (RCT) will be performed, with two additional patient preference arms ("patient preference randomized trial"). Patients who do not want to be randomized for treatment with one of the available therapies, will be asked to participate in the patient preference observational study. All patients will undergo a baseline evaluation and an assessment at the end of the 12-month follow-up (see figure 1 on page 15). A prolonged follow-up of 24 and 36 months will be evaluated too. A total of 66 patients will be included in the RCT and at least 120 patients are expected to take part in the patient preference part of the study.

For patients that do not want to take part in the patient preference randomized trial, the treating neurologist will be asked to fill in an anonymous questionnaire assessing general information in terms of age, sex, medication, age of onset PD, duration of PD, comorbidities and therapy of choice.

[figure not shown]
Because DBS and CLI are invasive treatments and both procedures have a (small) risk for irreversible and severe adverse events, it is not ethical to perform additional sham procedures. Therefore it is not possible to blind the patient for treatment assignment. As the primary health economic outcome and the primary clinical outcome are both based on patient-reported perceived quality of life measure (PDQ-39), a blinded endpoint assessment (PROBE-design) is not possible.

Rationale for the design

The RCT design in combination with an observational patient preference study was chosen because the studied therapies are available and differ largely. Currently, patients and neurologists together decide on what therapy to choose. Both patients and treating neurologists seem to have specific perceptions about the therapies. Consequently, the proportion of patients that is willing to be randomized between the two available treatments may be relatively small. This patient selection may restrict the generalization of the RCT results. Therefore, patients who are not willing to be randomized will be asked to take part in the patient preference observational study. These patients are allowed to receive their desired treatment without randomization and will be studied with respect to their baseline characteristics, primary clinical outcome and adverse events of the treatment. If the randomized patients resemble the non-randomized patients the RCT-results reflect a more accurate estimate of the treatment benefits and greater evidence of its external validity.

Version 7: 23-10-2019 13 of 48

Figure 1, flowchart

Version 7: 23-10-2019 14 of 48

4. STUDY POPULATION

4.1 Population (base)

Research population and source population

Patients with advanced PD who are eligible for treatment with both DBS and CLI. Adult patients will be recruited from academic and non-academic hospitals.

Feasibility

Currently, in the Netherlands, each year approximately 140 patients are eligible for treatment with DBS and CLI (all 80 patients yearly treated with DBS and approximately 80% of 80 patients yearly treated with CLI).

Approximately 160 are treated with DBS or CLI in the Netherlands yearly. We estimate that 140 patients will be eligible for the study and that 110 are initially treated in one of the participating centres. With a study duration of 33 months 302 patients will be eligible. This implies that a total of 66 patients (22% of eligible patients) will need to be randomized to assess cost-effectiveness of the treatments. This is a realistic goal because in the latest study in the same patient population, 58% of the eligible patients were recruited.[11]

For the two patient preference arms, we estimate that up to 180 patients will take part (i.e. 60% of the eligible population). It is our experience, from discussions with representatives of the Parkinson's disease association and in the outpatient clinic, that patients consider it important that more information on treatment of advanced PD becomes available.

Therefore, we think this is a realistic estimation. The burden of cooperation is low for the patient, especially since visits for the study will be combined with visits to the outpatient clinic for regular care or will be performed at home.

Characteristics of study population

PD is a disease of the elderly. We expect the population will be similar to the NSTAPS study, a study that was recently performed in the Academic Medical Center, comparing treatment with DBS in two different targets in the brain. In this study, the mean age was approximately 60 years, with a mean age of onset of PD of 49 years. In the NSTAPS study about 69% of the patients was male.[11]

4.2 Inclusion criteria

In order to be eligible to participate in this study, a subject must meet all of the following criteria:

Age > 18 years

Version 7: 23-10-2019 15 of 48

• idiopathic PD with bradykinesia and at least two of the following signs; resting tremor, rigidity, and asymmetry;

- despite optimal pharmacological treatment, at least one of the following symptoms: severe response fluctuations, dyskinesias, painful dystonia or bradykinesia;
- a life expectancy of at least two years.

4.3 Exclusion criteria

A potential subject who meets any of the following criteria will be excluded from participation in this study:

- · legally incompetent adults
- previous PD-neurosurgery (e.g., DBS, pallidotomy, thalamotomy);
- previous CLI (through a PEG-tube or Nasal Jejunal tube);
- contraindications for DBS surgery, such as a physical disorder making surgery hazardous;
- contraindications for PEG surgery such as interposed organs, ascites and oesophagogastric varices, or for Duodopa;
- Hoehn and Yahr stage 5 at the best moment during the day;
- other, severely disabling condition
- dementia or indication for severe cognitive impairment, such as PD-CRS <65
- psychosis;
- · current depression;
- pregnancy, breastfeeding, and women of child bearing age not using a reliable method of contraception;
- no written informed consent;
- · age below 18 years;

4.4 Sample size calculation

RCT

The primary objective of the study is to realize an efficient allocation of resources to the available treatment options in advanced PD. For this, primarily an economic evaluation will be carried out and the sample size has been calculated accordingly. Society's willingness-to-pay (WTP) per Quality Adjusted Life Year (QALY) may be indicative of whether or not CLI is affordable compared to DBS. The Dutch Raad voor de Volksgezondheid (RvZ) reported a value of €80,000 per additional QALY in 2006 as a potential upper limit of affordability. Explicitly, the figure is reported by the RvZ as a potential, but also unofficial limit: it should

Version 7: 23-10-2019 16 of 48

not be taken as a definite one. Other arguments based on patient preference or access to health care should be taken into account as well. Considering that CLI may be a less invasive intervention and access to health care is easier to facilitate when two interventions can be provided, a more lenient upper limit for the extra societal costs per additional QALY may be appropriate here. We propose a sample size calculation based on a WTP per additional QALY of €120,000 (50% above the RvZ figure). Based on the net health benefit formula suggesting that differences in QALYs between the interventions should be larger than the difference in costs (i.e., €34,174 a year) divided by the maximum WTP (i.e., €120,000 per QALY) in order for one intervention to be accepted as more efficient than another intervention, CLI treatment should at least outperform DBS treatment by 0.2847 QALY per year. Based on literature data with comparable costs estimates, [6] we anticipate standard deviations (SD) for QALYs up to 0.35 and for total costs up to €10,000 (factoring in a 12-month follow-up and non-responders).

To achieve 80% power and given a two-sided significance level of 0.05, up to 26 patients per group (or 52 in total) are needed to detect a difference of at least 0.2847 QALY for WTP-values up to €120,000 and a worst case scenario of zero correlation between costs and clinical effect, using a two-group t-test. Accounting for a possible dropout of 20%, we will randomize 66 patients (33 per group). With this sample size and given the same test conditions (power, type-I error rate, test chosen, drop-out rate) we are also able to detect a difference in mean PDQ-39 scores between both groups of 11.9, assuming an expected mean score of 32 in the DBS group and a standard deviation of 15.

Motivation for standard deviations for QALY

Literature data [8-10] show that the standard deviation for PDQ-39 scores from operated PD patients equals 15 points and that a 4 to 5 points difference is associated with a QALY difference of approximately 0.1,[16] suggesting a standard deviation for QALYs of up to 0.35.

Patient preference trial

We (conservatively) estimate that during the inclusion period a total of 180 patients (60% of the eligible patients) may decline to participate in the RCT, but are willing to take part in the preference observational study. Based on our clinical experience it is expected that 60% of these patients (n=108) prefers DBS, against 40% (n=72) preferring CLI.

When comparing the effect of DBS treatment of patients who express a preference for that treatment with the effect of DBS treatment in the randomised patients, and given the same test conditions (power, type-I error rate, two group t-test) we are able to detect a difference in

Version 7: 23-10-2019 17 of 48

mean PDQ-39 scores between both groups of 8,4, assuming an expected mean score of 32 in the randomized DBS group and a standard deviation of 15.

In case only 120 patients (40% of the eligible patients) agree to take part in the preference observational study, we are able to detect a difference in mean PDQ-39 scores between both DBS groups of 8,9.

When comparing the effect of CLI treatment for patients who express a preference for that treatment with the effect of CLI treatment in the randomised patients, and given the same test conditions (power, type-I error rate, chosen test) we are able to detect a difference in mean PDQ-39 scores between both groups of 8,9, assuming an expected mean score of 43,9 in the randomized CLI group and a standard deviation of 15. In case only 120 patients (40% of the eligible patients) agree to take part in the preference observational study, we are able to detect a difference in mean PDQ-39 scores between both CLI groups of 9,6.

Version 7: 23-10-2019 18 of 48

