Health Economics Analysis Plan

Version 1.0. Date March 18, 2022

This health economics analysis plan (HEAP) describes the plan to analyze and report the economic evaluation alongside the INVEST-study and should be considered an extension of the statistical analysis plan for the clinical outcomes. The reporting of this economic evaluation complies with the update CHEERS reporting standards 2022.²¹ Any deviations from the guideline were described and explained in full.

Dutch Trial Register: Identifier 4753, registered November 3, 2014
EudraCT: Number 2014–001501-32
Clinicaltrials.gov: NCT02480803
Sponsor protocol number: NL51240.018.14 INVEST study Version 7.0, October 23, 2019
Primary source of funding: ZonMw, The Netherlands Organization for Health Research and Development
Co-financier: Medtronic Europe
Trial protocol version: BMC Neurology 2020;20:40, PMID 32005175

The funding parties had no role in the design of the study, the HEAP, analyses, interpretation of data, or decision to submit results.

This HEAP was prepared by the INVEST core study group including
[name] PhD MD, neurologist (Chief investigator)
Prof. [name] PhD MD, neurologist
[name] MD, resident in neurology
[name] MSc, health scientist (author)
Prof. [name] PhD, health economist (guarantor)

Signatures

Author	Guarantor	Chief Investigator
		
[name] MSc	Prof. [name] PhD	[name] PhD MD
Date: March 18, 2022	Date: March 18, 2022	Date: March 18, 2022

For trial introduction and background, see the associated Statistical Analysis Plan INVEST included in this document, version 1.0. Date: March 18, 2022.

General characteristics

Aim

The aim of the economic evaluation was to answer the question: 'Is CLI treatment in PD patients associated with sufficiently higher quality adjusted life years when compared to DBS treatment, in order to justify its higher mean yearly costs?'

Objective

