For each of the 2,500 bootstraps the net health benefits (NHB) of CLI versus DBS were calculated based on the ICERs for different levels of willingness-to-pay up to €3,000 per additional unit decrease in change in PDQ-39 (NHB_{PDQ-39}), respectively based on the ICURs for willingness-to-pay levels up to €160,000. Cost-effectiveness acceptability curves were plotted to represent uncertainty,³⁶ showing the probability of CLI being cost-effective in comparison with DBS at each level of willingness to pay, see Figure EE-2.

Subgroup analyses

Considering the limited patient numbers, potentially uneven distributions of baseline characteristics despite randomization were exploratory addressed by subgroup analyses for hypothesis generation. Also, a preplanned subgroup analysis by median age was performed to detect a potential influence of being more vulnerable at a higher age.

Additional sensitivity analyses

Apart from addressing the uncertainty of missing data structures, additional sensitivity analyses were performed for the lengths of the life cycles of the DBS and CLI equipment and corresponding depreciation period (6 to 8 years in steps of 1 year versus 5 years).

Scenario analyses

A scenario analysis for the ICUR was performed to correct for health utility scores at baseline by subtracting for each patient the baseline score from the calculated QALYs during the follow-up of 12 months. Another scenario analysis was done to report the ICUR from an international perspective by applying the time trade-off based on valuation of health states based on preferences from the UK general population to the EQ-5D-3L health status profiles and conversion of Euros into English Pound by applying purchasing power parities from the Organisation of Economic Cooperation and Development (or 0.688 divided by 0.772 in 2020).^{37,38}

Table EE2a. Mean per patient use of hospital resources by strategy*

	CLI (n=)	DBS (n=)	Difference** CLI vs DBS
	Mean (95% BCa CI)	Mean (95% BCa CI)	Mean (95% BCa CI)
Screening for suitability			
preop. outpatient consultation			
inpatient stay			
on-/off-phase evaluation			
evaluation / nasogastric tube			
vitamin examinations			
other laboratory			
preop. anesthetic evaluation			
EKG			
MRI-brain	NA		
Continuous Levodopa Infusion			
CLI-pump			
CLI-cassettes			
PEG-jejunostomy placement			
tube replacement			
Deep Brain Stimulation			
(re)implantation			
electrode replacement			
extension cable replacement			
battery exchanges			

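### Protocol 4.4 calls zero cost-effect correlation the worst case for its 80% power, but on the net-health-benefit scale negative correlation is worse; the same sentence leaves the powered 0.2847 QALY ambiguous

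*Protocol*

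**What the plan says.** Protocol 4.4 starts from the net health benefit formula. It divides a yearly cost difference of €34,174 by a maximum willingness to pay (WTP) of €120,000 per QALY and concludes that "CLI treatment should at least outperform DBS treatment by 0.2847 QALY per year". For the variability, "we anticipate standard deviations (SD) for QALYs up to 0.35 and for total costs up to €10,000".

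It then states that, for 80% power at two-sided 0.05 with a two-group t-test, up to 26 patients per group "are needed to detect a difference of at least 0.2847 QALY for WTP-values up to €120,000 and a worst case scenario of zero correlation"; the correlation meant is that of costs with clinical effect. With 20% dropout this becomes 33 per group, 66 in total.

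Appendix 12.5 of the protocol plans the incremental analyses at €120,000 on net health benefit transformations and refers back to the sample size section for the threshold. In the HEAP, the aim is put as a question: "Is CLI treatment in PD patients associated with sufficiently higher quality adjusted life years when compared to DBS treatment", enough to justify the higher costs. Its incremental analysis bootstraps the NHB and plots acceptability curves "showing the probability of CLI being cost-effective in comparison with DBS at each level of willingness to pay".

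**The concern.** There are two difficulties in one sentence.

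- **The worst-case label.** The variance of NHB contains a covariance term with a negative sign. Negative correlation between costs and QALYs (sicker patients cost more and gain less) therefore increases the variance. Zero is the worst case only if negative correlation is excluded, and neither document gives a reason to exclude it. HEAP missing-data scenario (e) raises imputed costs and lowers imputed QALYs together. It concerns imputed values only, but it shows that the direction is not far-fetched.
- **The label on 0.2847.** The number first appears as the QALY gain at which CLI breaks even, and then as the difference the trial is powered to detect. WTP, cost SD and correlation have no role in a t-test on QALYs; they matter only for NHB. Section 4.4 does not say that the second use is an NHB difference, and it does not state the true QALY difference assumed under the alternative.

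At stake is how the stated power, and later an inconclusive or negative economic result, are read. The primary outcomes of this trial are economic, so readers need to know which conclusion had 80% power.

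**Working it through.** **Inputs, all from Protocol 4.4:** cost difference €34,174; WTP €120,000; SD of QALYs 0.35; SD of costs €10,000; correlation rho = 0; two-sided alpha 0.05; power 80%; 26 per group; 20% dropout. No other value of rho is documented, so -0.25 and -0.5 are my assumptions and -1 is a mathematical bound only.

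**Step 1: reproduce the plan.**

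- Difference: 34,174 / 120,000 = 0.28478 (the protocol truncates to 0.2847).
- Cost SD in QALY units: 10,000 / 120,000 = 0.0833.
- SD(NHB) = sqrt(0.35² + 0.0833² - 2 × rho × 0.35 × 0.0833). At rho = 0 this is sqrt(0.1225 + 0.0069) = 0.3598.
- Normal formula: n = 2 × ((1.960 + 0.842) × 0.3598 / 0.28478)² = 25.05, rounded up to 26 per group. Exact (noncentral t) power at 26 is 79.9%; 27 gives 81.4%.
- Dropout: 26 / 0.8 = 32.5, so 33 per group and 66 in total. The plan's figures are reproduced.

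**Step 2: is NHB the only reading?** A t-test on QALYs alone (SD 0.35) needs 23.71, so 24, by the normal formula, or 25 by exact t (80.5%); at 26 it has 82.0% power. The figure of 26 therefore does not prove NHB by itself. What favours NHB is that three of the listed inputs would otherwise be idle, and that appendix 12.5 plans the analysis on that scale.

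**Step 3: vary the correlation.** |NHB difference| = 0.28478, exact t:

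| rho | SD(NHB) | power, 26 per group | power, 33 per group |
|---|---|---|---|
| 0 | 0.3598 | 79.9% | 89% |
| -0.25 (assumed) | 0.3795 | 75.6% | 85% |
| -0.5 (assumed) | 0.3983 | 71.5% | 82% |
| -1 (bound) | 0.4333 | 64.2% | 75% |

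With 33 evaluable per group, power stays at or above 80% down to rho of about -0.62.

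**Step 4: what a 0.2847 NHB difference means in QALYs.** At the planned cost difference, NHB (CLI minus DBS) = true QALY difference - 0.28478. With 26 per group and rho = 0:

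| true QALY difference, CLI minus DBS | NHB | probability of rejecting zero NHB |
|---|---|---|
| 0 | -0.285 | 79.9% (CLI not cost-effective) |
| 0.1 | -0.185 | 44% |
| 0.2 | -0.085 | 13% |
| 0.2848 | 0 | 5% (2.5% in each direction) |
| 0.4 | 0.115 | 20% |
| 0.5 | 0.215 | 56% |
| 0.57 | 0.285 | 79.9% (CLI cost-effective) |

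The 80% thus holds at two mirror-image points, 0 and 2 × 0.28478 = 0.57.

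**Step 5: which point did the sponsor have in mind?** The documents point in different directions.

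- The introduction says that "when comparing individual studies, the effects on quality of life are similar", which suggests 0. The hypothesis in the summary, that "the surplus in costs is not cost-effective with regard to benefits for the patient and caregivers in quality of life", fits a verdict against CLI.
- Section 4.4 also uses expected PDQ-39 means of 32 for randomized DBS and 43.9 for randomized CLI. The HEAP (Health outcomes) codes higher as worse, so CLI is worse there. At the protocol's own 4 to 5 points per 0.1 QALY, 11.9 points is 0.24 to 0.30 QALY against CLI, where rejection against CLI exceeds 99.9%. However, 43.9 is exactly 32 + 11.9, the stated detectable difference, so it may not be a forecast.

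**The case against.** The strongest reply is that the documents already tie this calculation to NHB. Section 4.4 names the NHB formula just before the sentence at issue, appendix 12.5 refers back to it, and NHB is measured in QALYs, so the unit is correct. That stands, and it is why NHB is the better reading. But the formula is named only as the source of the threshold; it is not carried over to the quantity tested.

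A second reply is that rejecting at alpha when the truth lies on the null is how any test behaves and is no defect. That also stands. The difficulty is that one number serves both as the break-even gain and as the detectable difference. A reader might infer that the protocol claims 80% power to show CLI efficient at a gain of 0.2847 QALY. Section 4.4 makes no such explicit claim; its wording merely permits the inference.

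Third, the effect of correlation is undocumented and modest, and the HEAP runs no formal NHB test, so the rejection probabilities describe a test that supports the sample size rather than the planned report. This is fair and limits the severity. It does not rescue the worst-case label, which is wrong whatever the true rho is.

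**Conclusion.** The point holds as a minor wording fault with two parts.

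- Zero correlation is not the worst case. The 80% at 26 per group falls to about 76% at an assumed rho of -0.25 and 72% at -0.5. With all 33 per group evaluable it remains 85% and 82%.
- The detectable difference is not identified as an NHB difference, and the assumed true QALY difference is not stated. Under the NHB reading, 80% power belongs to a true difference of 0 or about 0.57 QALY, and there is no power at 0.2847.

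This rests on the protocol's SDs, the €34,174 cost difference, WTP €120,000 and the NHB reading, which is an inference.

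Three stronger conclusions might be drawn and are not supported. The sample size is not wrong: 66 follows from the stated inputs. The figure of 26 does not by itself prove an NHB test, since a QALY-only test needs 24 to 25 and the text says up to 26. Nor can equal QALYs be taken as the assumed alternative: the introduction leans that way, the PDQ-39 means do not, and 4.4 is silent.

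**What to change.** In Protocol 4.4, or in the HEAP under Cost-effectiveness threshold, delete the worst-case label and restate along these lines:

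> About 80% power (26 evaluable per group, two-sided 5%) for an absolute NHB difference of 0.2847 at €120,000 per QALY, assuming zero correlation between costs and QALYs. Negative correlation lowers power (assumed rho -0.25: 76%; -0.5: 72%). At the planned cost difference this corresponds to a true QALY difference, CLI minus DBS, of 0 (conclusion: CLI not cost-effective) or about 0.57 (conclusion: CLI cost-effective). A true gain of 0.2847 QALY is the break-even point, where there is no power.

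The sponsor should add which true QALY difference was assumed; it should not be filled in on the sponsor's behalf. The cost is a few lines of text. The sample size, inputs and planned analyses do not change.
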